4.10.3.2 Progression-free Survival (PFS)

Progression-Free Survival (PFS) is defined as the time to PFS event from first exposure to lerociclib. PFS event is defined as PD (per RECIST v1.1 as assessed by the investigator) or death due to any cause, whichever comes first. For participants without death or disease progression, PFS will be censored at the date of the last valid RECIST assessment unless otherwise stated. PFS duration will be calculated as

$$\text{Date of observation} - \text{Date of first exposure to lerociclib} + 1$$

where date of observation is the earliest of death, progression, or censoring.

PFS events and censoring rules, such as initiation of disallowed anticancer therapy, are defined below in Table 2.

All valid RECIST assessments after start of treatment will be used in the PFS analysis regardless of whether they were collected as part of scheduled or unscheduled visits. RECIST assessments based on scans performed after the end of lerociclib therapy will be used in the analysis of PFS if prior censoring events have not been observed.

Table 2 Censoring Rules for Progression-Free Survival

| Situation | Outcome | Date of Event/ Censoring |
|--|---------|---|
| PD or death, whichever occurred first, before exposure to subsequent antineoplastic therapy, withdrawal of consent, loss to follow up, data cutoff, or end of study. | Event | Earliest date of documented progression or death |
| No baseline disease assessment | Censor | Date of first exposure |
| No valid post-baseline tumor assessment | Censor | Date of first exposure |
| PD or death immediately after missing ≥ 2 consecutive scheduled tumor assessment | Censor | Date of last valid tumor assessment prior to the missing tumor assessments |
| No PD or death on or before 
 Database cut End of study Start of new antineoplastic therapy | Censor | Date of last tumor assessment on or prior to earliest censoring event listed in first column of this row. |

Descriptive summaries of time to event data will include median, twenty-fifth and seventy-fifth percentiles, and associated 2-sided 95% CIs based on Kaplan-Meier methods. Survival estimates along with corresponding 95% CIs using the log-log transformation will be provided at certain intervals as data allows.

A Kaplan-Meier plot will be presented and will include the number of participants at risk over time by line of therapy. No formal statistical hypothesis will be tested.

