9.3.3.3. Progression-free Survival and Overall Survival

Progression-free survival is measured from the date of the first dose of lerociclib in Cycle 1 until the date of the first documented disease progression or death. Diagnosis of PD will be based on RECIST v1.1; censoring methods for participants who do not experience PD or death will be described in the study SAP.

Overall survival is measured from the date of first dose of lerociclib until death. Censoring methods for participants who do not experience fatalities during the course of the study will be identified in the study SAP.

Descriptive summaries of time to event data will include median, 25th and 75th percentiles, and associated 2-sided 95% CIs based on Kaplan-Meier methods. Survival distribution function estimates along with corresponding 95% CIs using the log-log transformation will be provided at 6-month intervals as data allows. Kaplan-Meier plots of the survival distribution function will be presented and will include the number of participants at risk over time. No formal statistical hypothesis will be tested.

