6.2 Imputation Rules for Partial or Missing Dates

Imputation of partial dates will be made for AE onset and stop dates, start and end dates of concomitant medication, start date of subsequent therapy, and death date. If dates are completely missing, no imputation will be made. For any partial date with missing year, no imputation will be made.

The general rule for imputation is:

- If only day is missing, then the 15th of the month will be used.
- If only year is present, then June 30th will be used.

If such imputation date for diagnosis is on or after date of first dose, the date of first dose – 1 will be used.

If such imputed date for subsequent therapies is before date of last dose, the date of last dose + 1 will be used.

If the imputed date is for an AE start date and is in the same year and month as the first dose date but before the first dose date, the first dose date will be used, or if the imputed AE start date is after the AE end date, the AE end date will be used.

If the imputed date is for an AE start date and is in the same year and month as last dose date + 30 days but after the last dose date + 30 days, the last dose date + 30 days will be used.

If the imputed date is for an AE end date and is after the death date, the death date will be used, or if the imputed AE end date is before the AE start date, the AE start date will be used.

For the missing death dates, if death year and month are available but day is missing:

- If mmyyyy for last contact date still alive = mmyyyy for death date, set death date to the day after the last contact date.
- If mmyyyy for last contact date still alive < mmyyyy for death date, set death date to the first day of the death month.

If both month and day are missing for death date or a death date is entirely missing, do not impute and censor the participant survival time.

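### PFS Table 2 does not settle whether a death before the first post-baseline scan is an event or a Day 1 censoring, and Appendix 6.2 censors OS for known deaths that lack month and day or any date

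*SAP*

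**What the plan says.** **PFS.** SAP 4.10.3.2 gives the definition: "PFS event is defined as PD (per RECIST v1.1 as assessed by the investigator) or death due to any cause, whichever comes first". The general censoring sentence is confined to people without an event: "For participants without death or disease progression, PFS will be censored at the date of the last valid RECIST assessment unless otherwise stated". Protocol 9.3.3.3 runs PFS "until the date of the first documented disease progression or death" and leaves to the SAP only the censoring of participants who have neither.

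Table 2 in SAP 4.10.3.2 then lists situations. Counting below the header:

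- Row 1 is an event: "PD or death, whichever occurred first, before exposure to subsequent antineoplastic therapy, withdrawal of consent, loss to follow up, data cutoff, or end of study". No post-baseline scan is required.
- Row 2 censors at first exposure when there is no baseline disease assessment.
- Row 3 reads "No valid post-baseline tumor assessment | Censor | Date of first exposure".
- Row 4 censors progression or death that comes straight after two or more consecutive missed scheduled assessments, at the last valid assessment before the gap.

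Rows 2 and 3 do not mention death, and nothing says which row wins when two apply.

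**OS.** SAP 4.10.3.3 censors only participants who have not died. SAP Appendix 6.2 imputes a death date when only the day is missing, and that death stays an event. When month and day are both missing, or the whole date is, the instruction is "do not impute and censor the participant survival time". The general rule in the same appendix, whose list of imputed dates includes the death date, says: "If only year is present, then June 30th will be used".

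**The concern.** The first on-treatment scan falls in the window Study Day 50 to 64 (SAP 4.10.1.3). Someone who dies before it without an unscheduled scan meets row 1 and row 3 together. One gives an event on the date of death. The other gives a censored PFS of one day. Two programmers could both follow the SAP and produce different curves.

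For OS, the appendix turns a participant known to be dead into a censored observation, which the OS section does not provide for.

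Both departures act in the same direction. Removing a failure from a Kaplan-Meier estimate raises it, and in a single-arm study no control arm shares the error. SAP 4.13 states that the protocol's statistical methods are unchanged, so a reader would not expect deaths to be censored here.

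**Working it through.** **1. Which row governs an early death?** Three features of SAP 4.10.3.2 bear on this.

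- Row 4 names deaths that would usually also satisfy row 1. If row 1 took precedence, row 4 would do nothing for them. Row 4 therefore needs censoring rows to override row 1, and by the same logic row 3 would override it too.
- The date of observation is the earliest of death, progression and censoring. If row 3 supplies the date of first exposure, that date is always earliest.
- Against this, the event definition and the general censoring sentence keep death as an event, and row 4 mentions death where rows 2 and 3 do not.

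The text supports either reading.

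**2. Size for PFS.** The plan has no figure of its own on this point. Its one numerical precision statement (SAP 4.12: half-width of the 95% CI for ORR no larger than about 16% with about 40 participants) reproduces. Clopper-Pearson at 20 of 40 gives 33.8% to 66.2%, a half-width of 16.2 points. It does not depend on how deaths are handled.

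Inputs:

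- n = 50 per line of therapy (SAP 4.12).
- Median PFS 24 months (SAP 3.1.2, where it serves only to set study duration). The exponential shape is my assumption.
- k deaths before the first scan. The documents give no number, so k = 1, 2 and 3 are assumed.

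Let the other 50 − k participants follow S(t) = 0.5^(t/24).

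- Early deaths as events: (1 − k/50) × S(t).
- Early deaths censored on Day 1: S(t).
- Ratio of the two after the early period: 50/(50 − k).
- Median with deaths as events: 24 × ln(0.5/(1 − k/50))/ln(0.5).

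At 6 months S = 0.5^0.25 = 84.1%. Differences are taken from unrounded values.

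| k | 6-month PFS, events | 6-month PFS, Day 1 censored | Difference (points) | Median, events (months) | Median, censored (months) |
|---|---|---|---|---|---|
| 1 | 0.98 × 84.1 = 82.4% | 84.1% | 1.7 | 23.3 | 24.0 |
| 2 | 0.96 × 84.1 = 80.7% | 84.1% | 3.4 | 22.6 | 24.0 |
| 3 | 0.94 × 84.1 = 79.0% | 84.1% | 5.0 | 21.9 | 24.0 |

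A simulation of 1,000 trials per k gave the same 6-month differences (1.7, 3.4 and 5.0 points).

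**3. Which k is plausible?** Under the same model, the chance of any PFS event (progression or death) by Day 57 is 1 − 0.5^(1.873/24) = 5.3%, where 57/30.4375 = 1.873 months. That is 2.6 of 50 participants, and by Day 64 it is 2.9. Deaths are only part of these, so k = 1 or 2 is more realistic than 3.

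**4. OS.** The direction is upward because a failure is removed. The size depends on how many deaths lack month and day or any date, and on when they occur. The documents give neither, so no figure is offered.

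**The case against.** The strongest reply on PFS is that the SAP already answers the question. Death is an event, general censoring is for people without one, and row 1 comes first in the table. Where the authors want to censor a death, in row 4, they say so. This stands far enough to defeat the stronger claim a reader might infer, that Table 2 plainly censors every early death on Day 1. It does not remove the conflict, because giving row 1 priority would disable row 4.

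On OS, a reader might infer that any incomplete death date leads to censoring. That is wrong: a missing day alone is imputed and the death counts. The clash with the 30 June rule can also be answered in part, since a death-specific rule would normally govern over a general one. The contradiction with SAP 4.10.3.3 remains.

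Few participants should be affected:

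- Protocol 5.1 requires ECOG 0 or 1, and Protocol 5.2 excludes symptomatic visceral disease.
- A screening tumor evaluation is scheduled for everyone, so row 2 should be nearly empty.
- Scans are planned at end of treatment, and Protocol 7.1.1 asks for one when treatment stops for reasons other than progression and there is no recent scan. Unscheduled and post-treatment scans count for PFS.
- Protocol 7.3 allows public sources to be searched for vital status, and Protocol 8.3 asks for death documentation.

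All of this limits the likely size. It does not tell the programmer what to do when a case arises.

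**Conclusion.** The concern holds as an unresolved conflict for PFS and as a narrow but explicit contradiction for OS.

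For PFS, one reasonable reading of Table 2 censors deaths before any post-baseline scan on Day 1, contrary to the SAP's event definition and Protocol 9.3.3.3. Each such death would raise 6-month PFS in its line of therapy by about 1.7 points. That figure rests on 50 participants per line, an exponential curve with a 24-month median for the rest, and an assumed number of deaths. For OS, the rule reaches only deaths lacking both month and day, or any date.

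A reader might also infer that deaths disappear from the safety evaluation. They do not: SAP 4.9.2 tabulates fatal TEAEs, summarizes deaths by line of therapy and cause, and lists every death. The primary endpoint, incidence of AEs and SAEs, is untouched. Because PFS and OS are secondary and descriptive with no hypothesis test, this is a should-fix, best settled before database lock so that the choice is not made with the deaths in view.

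**What to change.** **Table 2 (SAP 4.10.3.2).** Add the condition *and no death* to rows 2 and 3. State that a death not preceded by one of the row 1 cut-offs, and occurring before two consecutive scheduled assessments have been missed, is an event on the date of death. With assessments expected on Day 57 and Day 113 (57 + 56) and a window of 7 days, the second one is not missed until after Day 120. State also that a later death without any post-baseline scan follows the missed-assessment rule in row 4, and name the censoring date for that case, since there is no post-baseline assessment to fall back on. Simply declaring that row 1 takes precedence is not enough, because it would cancel row 4.

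**Appendix 6.2.** Keep every known death as an OS event. If month and day, or the whole date, are missing, impute the day after the participant was last known alive, inside the known year where one is given and no later than data cutoff. Add a sensitivity analysis with a later date, such as the next scheduled 12-week survival contact. Exempt death dates from the 30 June rule so that only one rule applies.

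**Cost.** A few lines of SAP text and minor programming. The descriptive PFS and OS estimates may come out slightly less favourable.

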4.10.3.3 Overall Survival (OS)

OS is defined as the time to death by any cause from first exposure to lerociclib. Participants who have not died will be censored at the last contact date at which the participant is known to be alive.

Descriptive summaries of time to death data will include median, twenty-fifth and seventy-fifth percentiles, and associated 2-sided 95% CIs based on Kaplan-Meier methods. Overall survival estimates along with corresponding 95% CIs using the log-log transformation will be provided at certain intervals.

A Kaplan-Meier plot of the survival distribution will be presented and will include the number of participants at risk over time by line of therapy. No formal statistical hypothesis will be tested.

4.10.3.4 Duration of Response (DOR)

Only participants who have a confirmed response will be included in the analysis of DOR. DOR is defined as the time to PFS Event from first confirmed response. DOR will start at the time of the initial response and not the time for the confirmatory scan.

The definition of the end of DOR is the same as PFS Event, and the censoring rules will be the same as shown in Table 2 above.

Descriptive summaries of time to event data will include median, twenty-fifth and seventy-fifth percentiles, and associated 2-sided 95% CIs based on Kaplan-Meier methods.

A Kaplan-Meier plot will be presented and will include the number of participants at risk over time by line of therapy. No formal statistical hypothesis will be tested.

4.10.3.5 Time to Response (TTR)

Only participants who have a confirmed response (CR or PR) will be included in the analysis of TTR. TTR is defined as the time from first exposure to lerociclib to first confirmed response.

Descriptive summaries of time to response data will be presented.

4.11 Other Analyses

4.11.1 Pharmacokinetics

The detailed procedures for the pharmacokinetic endpoints will be described in a separate Pharmacometric Analysis Plan.

4.11.2 Patient Reported Outcome (PRO) Measures

Health-related quality of life (HR-QoL) will be assessed using the following measures:

- EORTC-QLQ-C30
- EORTC-QLQ-BR23
- EQ-5D-5L
- FACIT Item GP-5

4.11.2.1 EORTC QLC-C30 and EORTC QLQ-BR23

The EORTC-QLQ-C30 was developed to assess HR-QoL, functioning, and symptoms in cancer clinical trials. It consists of 30 questions, which can be grouped to produce five multi-item functional scales, three multi-item symptom scales, six individual items (five items assessing additional symptoms commonly reported by cancer patients and one item on the financial impact of the disease), and a two-item global measure of health status/quality of life:

- Functional scales:
 - Physical functioning
 - Role functioning
 - Emotional functioning
 - Cognitive functioning
 - Social functioning
- Multi-item symptom scales:

- Fatigue
- Nausea and vomiting
- Pain
- Individual items:
 - Dyspnoea
 - Insomnia
 - Appetitive loss
 - Constipation
 - Diarrhoea
 - Financial difficulties
- Global health status/quality of life

The EORTC QLQ-BR23 is a breast cancer-specific module used to assess breast cancer-specific HR-QoL. It comprises 23 questions which can be grouped into five multi-item scores (body image, sexual functioning, arm symptoms, breast symptoms, and systemic therapy side effects) and single items on sexual enjoyment, upset by hair loss and future perspective. This instrument can be combined in four functional scales and four symptom scales:

- Functional scales:
 - Body image
 - Sexual functioning
 - Sexual enjoyment
 - Future perspective
- Symptom scales
 - Systemic therapy side effects
 - Breast symptoms
 - Arm symptoms
 - Upset by hair loss

An outcome variable consisting of a score from 0 to 100 will be derived for each of the functional scales, symptom scales, individual items, and global health status/ QoL in the EORTC QLQ-C30 and for each of the functional and symptom scales for the EORTC QLQ-BR23 according to the EORTC QLQ-C30 Scoring Manual and EORTC QLQ-BR23 instructions.

Higher scores on the global health status/QoL and functioning scales indicate better health status/functioning. Higher scores on the symptom scales indicate greater symptom burden.

For all scales, if at least half the components of a scale are present for a timepoint then the score will be calculated, otherwise the score will be set to missing.

The principle for scoring the scales of the QLQ-C30 and QLQ-BR23 are:

- Estimate the average of the items that contribute to the scale (raw score)

- Use a linear transformation to standardize the raw score, so that the scores range from 0 to 100

In practical terms, if terms I_1, I_2, \dots, I_n are included in a scale, then:

$$RS = \frac{\sum_{i=1}^n I_i}{n}$$

where RS denotes the raw score.

All functional scales are then calculated as $S = \left\{1 - \frac{RS-1}{range}\right\} * 100$ and symptom scales, items, and global health status as $S = \left\{\frac{RS-1}{range}\right\} * 100$.

Range is defined as the difference between the maximum possible value of RS and minimum possible value of RS for the specified scale.

The global health status/QoL, functional scales, and symptom scales, including the items included in each of these scales, are presented in Table 3 and Table 4.

Table 3 Scoring the QLQ-C30

| | Scale | Number of Items | Item | Item Numbers |
|-----------------------------|-------|-----------------|------|--------------|
| Global Health Status | | | | |
| Global Health Status | QL2 | 2 | 6 | 29, 30 |
| Functional Scales | | | | |
| Physical | PF2 | 5 | 3 | 1 – 5 |
| Role | RF2 | 2 | 3 | 6, 7 |
| Emotional | EF | 4 | 3 | 21 – 24 |
| Cognitive | CF | 2 | 3 | 20, 25 |
| Social | SF | 2 | 3 | 26, 27 |
| Symptom Scales/Items | | | | |
| Fatigue | FA | 3 | 3 | 10, 12, 18 |
| Nausea & Vomiting | NV | 2 | 3 | 14, 15 |
| Pain | PA | 2 | 3 | 9, 19 |
| Dyspnoea | DY | 1 | 3 | 8 |
| Insomnia | SL | 1 | 3 | 11 |
| Appetite loss | AP | 1 | 3 | 13 |
| Constipation | CO | 1 | 3 | 16 |
| Diarrhoea | DI | 1 | 3 | 17 |
| Financial difficulties | FI | 1 | 3 | 28 |

a. Item range is the difference between the possible maximum and the minimum response to individual items; most items take values from 1 to 4, giving range = 3.

Table 4 Scoring the QLQ-BR23

| | Scale | Number of Items | Item | Item Numbers |
|---------------------------------|-------|-----------------|------|--------------|
| Functional Scales | | | | |
| Body image | BRBI | 4 | 3 | 9 – 12 |
| Sexual functioning ^d | BRSEF | 2 | 3 | 14, 15 |
| Sexual enjoyment ^{b,d} | BRSEE | 1 | 3 | 16 |
| Future perspective | BRFU | 1 | 3 | 13 |

| Symptom Scales/Items | | | | |
|---------------------------------|------|---|---|--------------|
| Systemic therapy side effects | BRST | 7 | 3 | 1 – 4, 6 – 8 |
| Breast symptoms | BRBS | 4 | 3 | 20 – 23 |
| Arm symptoms | BRAS | 3 | 3 | 17 – 19 |
| Upset by hair loss ^c | BRHL | 1 | 3 | 5 |

a. Item range is the difference between the possible maximum and the minimum response to individual items; most items take values from 1 to 4, giving range = 3.

b. Not applicable if item 15 is “not at all”.

c. Not applicable if item 4 is “not at all”.

d. Items for these scales are scored positively (ie, “very much” is best) and therefore use the same scoring methodology as for symptom scales.

For all EORTC QLQ-C30 and BR23 scores, a clinical meaningful change or difference in score will be defined as a change of at least 10 points [3]. Specifically, a clinically meaningful improvement in a symptom will be defined as a decrease in the score from baseline of ≥ 10 , whereas a clinical meaningful deterioration will be defined as an increase in the score from baseline of ≥ 10 . In contrast, a clinical meaningful improvement in a functional scale or global health status/ QoL score will be defined as an increase in the score from baseline of ≥ 10 , while a clinically meaningful deterioration in a functional scale or global health status/ QoL will be defined as a decrease in the score from baseline of ≥ 10 .

Descriptive statistics for subscale scores, including changes from baseline, will be presented by visit and line of therapy. Plots of mean change from baseline in total and subscale scores over time will also be presented with indicators for the number of patients at each visit.

In addition, the proportion of patients experiencing improvement, no change or worsening from baseline will be presented by visit and line of therapy. Improvement, no change, and worsening will be defined as shown in Table 5 for all subscales.

Table 5 Change from Baseline Classification (EORTC QLC-C30, EORTC QLQ-BR23)

| Score | Change from Baseline | Visit Response |
|--|----------------------|----------------|
| Symptom scales/items | Change $\geq +10$ | Worsened |
| | Change ≤ -10 | Improved |
| | Otherwise | No Change |
| Functional scales and global health status/QoL | Change $\geq +10$ | Improved |
| | Change ≤ -10 | Worsened |
| | Otherwise | No Change |

4.11.2.2 EQ-5D-5L

The EQ-5D-5L is comprised of six questions that cover 5 dimensions of health:

- Mobility
- Self-care
- Usual Activities
- Pain/Discomfort
- Anxiety/Depression

For each dimension, patients select which statement describes their health on that day from a possible five options of increasing levels of severity (no problems, slight problems, moderate problems, severe problems, and unable to/extreme problems). A unique EQ-5D health state, termed the EQ-5D-5L profile, is reported as a five-digit code with a possible 3,125 health states. For example, state 11111 indicates no problems on any of the five dimensions.

Patients will also assess their current health using the EQ-VAS which ranges from 0 (worst imaginable health) to 100 (best imaginable health).

The EQ-5D profile will be converted into a weighted health state utility value, termed the EQ-5D index, by applying a country-specific equation to the EQ-5D-5L profile that represents the comparative value of health states. The equation is based on national valuation sets elicited from the general population, and the base case will be the United Kingdom perspective. Where a valuation set has not been published, the EQ-5D-5L profile will be converted to the EQ-5D index using a crosswalk algorithm [4]. If an EQ-5D-5L value set does not exist for a country and neither does the EQ-5D-3L value set for use with the crosswalk algorithm, then a value set for a country that most closely resembles the country missing will be used.

Results from the EQ-5D-5L will be summarized descriptively by visit, including a shift table from baseline to worst on treatment for each dimension of health. Worst on treatment is defined as the highest numerical state for each dimension scored while on treatment (e.g., 2 is worse than 1). Plots of mean change from baseline in EQ-VAS and health state utility value over time will also be presented with indicators for the number of patients at each visit.

